- 11. Congestive heart failure (New York Heart Association Class III or IV) or unstable angina pectoris; previous history of myocardial infarction within one year prior to study entry, uncontrolled hypertension, or uncontrolled arrhythmias (see Appendix 5)
- 12. Patients with a family history of QT prolongation
- 13. Concomitant medication(s) known to cause Torsades de Pointes (TdP) initiated less than the duration required to reach steady-state plasma concentration (approximately five half-lives)before first dose of study drug (see Appendix 6) (medications used as needed [PRN] (e.g. Zofran) are exempt)
- 14. Concurrent treatment with chronic corticosteroids except if chronic treatment with < 20 mg of methylprednisolone daily or equivalent (pulse steroids for treatment or prophylaxis are allowed [e.g., for transfusion or medication reactions])
- 15. Known HIV positivity
- 16. Active, uncontrolled bacterial, viral, or fungal infections, requiring systemic therapy (prophylactic systemic antimicrobials permitted)

- 17. Uncontrolled disease-related metabolic disorder (e.g., hypercalcemia)
- 18. Pregnant or nursing women or women of childbearing potential not using highly effective contraception; male patients not using highly effective contraception Note: Women of childbearing potential (see Section 5.6) and men must agree to use highly effective contraception (see Section 5.6.1) prior to study entry and for the duration of study participation and 90 days after.
 - Should a woman become pregnant or suspect she is pregnant while participating in this study, she should inform her treating physician immediately.
- 19. Serious nonmalignant disease (e.g., hydronephrosis, liver failure, or other conditions) that could compromise protocol objectives in the opinion of the Investigator and/or the Sponsor
- 20. Unwillingness or inability to comply with procedures either required in this protocol or considered standard of care
- 21. Medical, uncontrolled disease-related metabolic disorder, psychiatric, cognitive, or other conditions that may compromise the patient's ability to understand the patient information, give informed consent, comply with the study protocol, or complete the study
- 22. History of severe allergic reaction to azacitidine (if patient enrolling into azacitidine combination cohort) or low-dose cytarabine (if patient enrolling into cytarabine combination cohort)

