5.6 Childbearing Potential

For all patients of childbearing potential, all methods of contraception, including abstinence, must be in use from the time of consent through the final study visit, and for 90 days after the last dose of study drug. Patients who are not sexually active during the Screening Period must agree to the contraceptive requirements if they become sexually active with a partner of the opposite sex during the study and for 90 days after the last dose of study drug. Unique situations that may not fall within these specifications may be discussed with the Forma Therapeutics Medical Monitor on an individual basis.

Female patients will be considered of childbearing potential after the onset of their first menstrual period. Female patients who are documented as being of nonchildbearing potential

(postmenopausal or having undergone surgical sterilization) are exempt from this requirement. Female patients will be considered postmenopausal if they have had 12 months of consecutive spontaneous amenorrhea or less than 12 months of consecutive spontaneous amenorrhea and a serum FSH level > 40 mIU/mL at Screening. Female patients will be considered surgically sterile if they are post-hysterectomy, 6 months post-surgical bilateral oophorectomy, or 6 months post-tubal ligation.

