- To be performed on all female patients of childbearing potential and within 72 hr of dosing (Day 1 only of every cycle). At Screening, women aged 55 and under, are not surgically sterile, and who are amenorrheic must have LH, FSH, and estradiol measurements within the postmenopausal range for the institution, to be considered of nonchildbearing potential. A serum pregnancy test is required at Screening; serum or urine pregnancy tests are allowed for post-Screening visits.
- Phase 1: Electrocardiograms will be performed in triplicate (within a 10-minute period) predose and at 2 (± 15 minutes), 4 (± 15 minutes), and 8 hr postdose (± 30 minutes) on Cycle 1 Day 1 and Cycle 2 Day 1, and predose at all study visits where indicated. Phase 2: Electrocardiograms will be performed in triplicate (within a 10-minute period) predose on Cycle 1 Day 1 and Cycle 2 Day 1, and at all study visits where indicated. All electrocardiograms will be performed in a supine position.

 Electrocardiograms performed as clinically indicated for Cycle 5 and beyond.
- ^m 24-hour 12-lead continuous Holters will be collected on C1D1 and C2D1 for patients at all centers in the US and select centers ex-US. The Holters should run from approximately 1 hour before dosing until 24 hours (the next day). Patients should remain supine for 10-15 minutes before and 5 minutes after ECG collection. See manual for further guidance on Holter monitoring.
- ⁿ Clinical serum chemistries to include Na, K, Cl, bicarbonate, Mg, Ca, BUN, creatinine, AST, ALT, ALP, albumin, total bilirubin, direct bilirubin (collected only if total bilirubin is abnormal), LDH, glucose, amylase, lipase, uric acid, and thyroid function test (TFT) panel, which includes thyroid-stimulating hormone, free T3, and T4. In addition to the other chemistry panels, TFT panel is to be completed at Screening, C1D1, C2D1, and C3D1, then as clinically indicated.
- ^o May be performed from 48 hr (Cycle 2) or 72 hr (Cycle 3 and 4) prior to Day 1 of a cycle (see Section 6.1).
- P Clinical serum chemistries and CBC with differential and platelet count only at these study visits. May be performed through local laboratory testing.
- ^q Includes hemoglobin, hematocrit, platelets, and white blood cell count with differential.
- ^r Includes PT and PTT.
- Bone marrow aspirate for response assessment as described in Section 4.3. Refer to the laboratory manual for details of sample collection timing.

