- Includes complete surgical and cardiac history and complete leukemia medical history. Complete leukemia medical history will include applicable treatment history as well as cytogenetic risk categorization at diagnosis by NCCN or ELN guidelines.
- f Height at Screening only.
- g Includes predose temperature, blood pressure, pulse rate, and respiratory rate.
- h Symptom-directed physical examination due to specific findings or abnormalities.
- To be performed on all female patients of childbearing potential and within 72 hr of dosing (Day 1 only of every cycle). At Screening, women aged 55 and under, are not surgically sterile, and who are amenorrheic must have LH, FSH, and estradiol measurements within the postmenopausal range for the institution, to be considered of nonchildbearing potential. A serum pregnancy test is required at Screening; serum or urine pregnancy tests are allowed for post-Screening visits.
- j Electrocardiograms performed as clinically indicated.
- ^k Clinical serum chemistries to include Na, K, Cl, bicarbonate, Mg, Ca, BUN, creatinine, AST, ALT, ALP, albumin, total bilirubin, direct bilirubin (collected only if total bilirubin is abnormal) conducted as indicated.
- Clinical serum chemistries also include LDH, glucose, amylase, lipase, uric acid, and thyroid function test (TFT) panel (including thyroid-stimulating hormone, free T3, and T4) conducted at Screening then as clinically indicated.
- m Includes hemoglobin, hematocrit, platelets, and white blood cell count with differential.
- n Includes PT and PTT.
- Bone marrow aspirate for response assessment to be done at Screening (if not taken at End of Treatment prior to roll-over) and then every 6 cycles unless there is suspicion of relapse/progression (see Section 4.3). Refer to the laboratory manual for details of sample collection timing.
 - Local IDH confirmation may have occurred > 28 days prior.
 - Patients who discontinue study treatment for reasons other than treatment failure and have not withdrawn consent from overall study participation, should continue to be followed for disease response assessments until the time of disease progression/relapse or the initiation of a new treatment regimen. Patients who have stopped FT-2102 treatment for HSCT should continue to be followed until disease progression/ relapse. This information should be documented on the appropriate eCRF page

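### Section 5.6 and the pregnancy-test footnotes of Appendices 1 and 2 define nonchildbearing potential differently for some amenorrheic women aged 55 and under

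*Protocol*

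**What the plan says.** Protocol Section 5.6 exempts from contraception women documented as postmenopausal or surgically sterilized. It gives two routes to postmenopausal status. The first is duration alone: "Female patients will be considered postmenopausal if they have had 12 months of consecutive spontaneous amenorrhea". The second is "less than 12 months of consecutive spontaneous amenorrhea and a serum FSH level > 40 mIU/mL at Screening". Neither route has an age limit, and neither mentions LH or estradiol.

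The footnote to the pregnancy-test row of Appendix 1 sets, at Screening, a different test: "women aged 55 and under, are not surgically sterile, and who are amenorrheic must have LH, FSH, and estradiol measurements within the postmenopausal range". Appendix 2 carries the same rule and states its purpose: women who are "amenorrheic must have LH, FSH, and estradiol measurements within the postmenopausal range for the institution, to be considered of nonchildbearing potential". The footnotes give no length of amenorrhea and no numerical FSH cutoff, and do not say that the amenorrhea must be spontaneous. The test itself is for women of childbearing potential.

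Neither text refers to the other. Exclusion criterion 18 points to Section 5.6 only: "Women of childbearing potential (see Section 5.6) and men must agree to use highly effective contraception". Inclusion criterion 11 (negative serum pregnancy test) and the ova-donation part of criterion 13 depend on childbearing potential without citing a definition. Criterion 12 (contraception) is worded in terms of fertility.

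**The concern.** Two passages of one protocol answer the same question about the same patient, and their answers can differ. Section 5.6 states conditions that are enough for postmenopausal status. The footnotes state a condition that must be met before a woman aged 55 or under can be called nonchildbearing. If 12 months of amenorrhea is enough, three hormone results cannot also be required.

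The classification decides whether a woman must use contraception until 90 days after the last dose, whether inclusion criterion 11 applies to her, and whether she is pregnancy-tested on treatment. FT-2102 is dosed continuously, and four of the eight Phase 2 cohorts (4, 5, 6 and 8) add azacitidine. Section 5.6.1 does not accept hormonal contraceptives as effective for female patients, so the obligation has practical weight. Sites reading different sections could classify the same woman differently.

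**Working it through.** No arithmetic applies. The check is to apply each definition to the same hypothetical women, all amenorrheic and not surgically sterile. Ages and hormone values are illustrative.

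| Case | Section 5.6 | Footnotes | Conflict? |
|---|---|---|---|
| A. Age 52, 12 months of spontaneous amenorrhea, hormones not measured or one out of range | Postmenopausal, exempt from contraception | Childbearing potential, pregnancy-tested | Yes |
| B. Age 52, 6 months of spontaneous amenorrhea, FSH 45 mIU/mL, estradiol out of range | Postmenopausal, exempt | Childbearing potential, tested | Yes |
| C. Age 52, 6 months of spontaneous amenorrhea, FSH at or below 40 or not measured, panel incomplete or not all in range | Childbearing potential (neither route met) | Childbearing potential | No |
| D. Age 52, amenorrhea not spontaneous, all three hormones in range | Childbearing potential (neither route met) | Nonchildbearing | Yes, reversed |
| E. Age 52, 6 months of spontaneous amenorrhea, all three in range, FSH below 40 | Childbearing potential | Nonchildbearing | Yes, reversed |
| F. Over 55 | Section 5.6 applies | No hormone rule | No |

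Cases A and B follow directly from the wording: both Section 5.6 routes can be met by a woman who fails the footnote.

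Cases D and E need the footnote to be read as a complete test, so that an in-range panel settles the matter. Case E also needs an institution whose postmenopausal FSH range starts below 40 mIU/mL. The documents do not give institutional ranges, so that is an assumption. Case D needs women whose amenorrhea has another cause, such as earlier treatment. The protocol admits relapsed, refractory and post-transplant patients but does not say how many have such amenorrhea.

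Cases C and F mark the boundary. The conflict lies among women aged 55 and under who satisfy one definition and fail the other.

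On whether the tests would be done: Section 6.1.3 does not name LH, FSH or estradiol, and neither do the chemistry panels. However, Section 6.1.3 runs its evaluations according to the schedule of events, and the footnote to the schedule's pregnancy-test row requires the three hormones at Screening.

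**The case against.** The strongest reply is that the footnote is the more specific text, and that a site can meet both passages by applying every obligation either one imposes. Section 5.6 also sends situations outside its specifications to the Medical Monitor. On that view nobody is under-protected. This holds for a site that reads both passages and always takes the more demanding result. But the protocol states no such order of precedence, exclusion criterion 18 cites Section 5.6 alone, and in cases D and E the more demanding passage changes. Cases A and B are also not outside Section 5.6: it classifies them plainly.

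A second reply is limited reach. Under Section 6.1, Appendix 1 now covers ongoing patients, who are past screening. Appendix 2 covers later enrollment, for which the example given is transfer from Cohort 1 to Cohort 3 or 6. That lowers the number of new classifications. It does not remove the point, since Appendix 2 repeats the footnote and both contraception and pregnancy testing continue on treatment.

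Three stronger readings are tempting, and the documents do not support them:

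- A reader might infer that sites would not order the hormone tests. The schedule footnote requires them at Screening, and Section 6.1.3 invokes the schedule. The screening list merely fails to repeat them.
- A reader might infer that pregnancy follow-up depends on the classification. Section 7.2.5 requires reporting of any pregnancy in a patient or a male patient's partner.
- A reader might infer that every amenorrheic, non-sterile woman aged 55 or under without a full postmenopausal panel is affected. Case C shows otherwise: a woman who also meets neither Section 5.6 route is of childbearing potential under both texts.

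**Conclusion.** The contradiction is real and confined to amenorrheic, non-surgically-sterile women aged 55 and under. The clear conflict concerns those who meet a Section 5.6 route but whose LH, FSH and estradiol are missing or not all in the institution's range. A reversed conflict is possible under the assumptions stated for cases D and E. The documents give no count; the number is probably small.

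This is an internal inconsistency bearing on patient protection. It does not touch sample size, error rates or any analysis. The SAP's Appendix 1 reproduces the footnote, but the SAP states that it is based on protocol version 5, and it does not govern eligibility or contraception. The copy therefore adds no separate problem. The point merits correction because the remedy is simple, and it implies no view on which definition is clinically right.

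**What to change.** Reconcile Section 5.6 with the footnotes of Appendices 1 and 2 into a single definition of nonchildbearing potential. Have inclusion criteria 11 to 13, exclusion criterion 18, the contraception section and the pregnancy-test rows all cite it. If the definition uses hormone values, repeat those tests in the Section 6.1.3 screening list, which now reaches them only through the schedule footnote. Which definition should stand is for the sponsor to decide.

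The cost is protocol wording and, depending on the definition chosen, perhaps one screening blood test for a few women. No statistical section needs to change.

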Appendix 2 Schedule of Events (Patients Enrolled After Protocol Version 7/ Amendment 6)

Study Procedures	Screening (D. 144), P.1	Cycle 1 and beyond	End of Txb	28-day Follow- up ^c	Survival Follow-up
Days	(D -14 to D1)	D1 ± 3D Every other cycle ^a	± 7D	+ 7D	q 3 mo
Signed Informed Consent ^d	X ^d				
Complete Medical History ^e	X				
Concomitant Medications	X	X	X	X	
Height and Weight ^f	X	X	X		
Vital Signs ^g	X	X	X		
ECOG PS	X	X	X		
Physical Examination	X	X ^h	X		
Serum or Urine Pregnancy Testi	X	X	X		
12-lead ECG	X	As clinically indicated	\mathbf{X}^{j}		
Clinical Serum Chemistries ^{k,l}	X	X	X		
CBC with Differential and Platelet Count ^m	X	X	X		
Coagulation Parameters ⁿ	X	As clinically indicated			
Bone Marrow Aspirate ^o	X	X	X		
AE Monitoring		Continuous	•	X	
Study Drug Diary ^p		X			
Study Drug Admin ^{q,r}		Drug will be given in accordance with the dosing schedules for FT-2102 and azacitidine			
Survivals					X

Admin = administration; AE = adverse event; ALT = alanine aminotransferase; ALP = alkaline phosphatase; AST = aspartate aminotransferase; BUN = blood urea nitrogen; C1D1 = Cycle 1 Day 1; C2D1 = Cycle 2 Day 1; Ca = calcium; CBC = complete blood count; Cl = chloride; ECG = electrocardiogram; ECOG PS = Eastern Cooperative Oncology Group performance status; FSH = follicle-stimulating hormone; K = potassium; LDH = lactate dehydrogenase; LH = luteinizing hormone; Mg = magnesium; Na = sodium; PT = prothrombin time; PTT = partial thromboplastin time; Tx = treatment.

NOTE: All assessments will be conducted predose unless specified otherwise.

- ^a Scheduled assessments will be performed every 2 cycles.
- End of Treatment visit to be conducted within 7 days of the decision to discontinue treatment. End of Treatment assessments need not be repeated if they were completed within the previous 2 weeks (4 weeks for bone marrow assessments).
- ^c 28-day Follow-up visit to be conducted within 28 days (+ 7 days) of last dose for adverse event follow-up and to capture initiation of new therapies (con-medications).
- Informed consent must be completed prior to the initiation of any study-specific procedures or assessments. The informed consent process may be completed prior to the Screening Period (i.e., before Day -14) (see Section 6.1.2).

- Includes complete surgical and cardiac history and complete leukemia medical history. Complete leukemia medical history will include applicable treatment history as well as cytogenetic risk categorization at diagnosis by NCCN or ELN guidelines.
- f Height at Screening only.
- g Includes predose temperature, blood pressure, pulse rate, and respiratory rate.
- h Symptom-directed physical examination due to specific findings or abnormalities.
- To be performed on all female patients of childbearing potential and within 72 hr of dosing (Day 1 only of every cycle). At Screening, women aged 55 and under, are not surgically sterile, and who are amenorrheic must have LH, FSH, and estradiol measurements within the postmenopausal range for the institution, to be considered of nonchildbearing potential. A serum pregnancy test is required at Screening; serum or urine pregnancy tests are allowed for post-Screening visits.
- j Electrocardiograms performed as clinically indicated.
- ^k Clinical serum chemistries to include Na, K, Cl, bicarbonate, Mg, Ca, BUN, creatinine, AST, ALT, ALP, albumin, total bilirubin, direct bilirubin (collected only if total bilirubin is abnormal) conducted as indicated.
- Clinical serum chemistries also include LDH, glucose, amylase, lipase, uric acid, and thyroid function test (TFT) panel (including thyroid-stimulating hormone, free T3, and T4) conducted at Screening then as clinically indicated.
- m Includes hemoglobin, hematocrit, platelets, and white blood cell count with differential.
- n Includes PT and PTT.
- Bone marrow aspirate for response assessment to be done at Screening (if not taken at End of Treatment prior to roll-over) and then every 6 cycles unless there is suspicion of relapse/progression (see Section 4.3). Refer to the laboratory manual for details of sample collection timing.
 - Local IDH confirmation may have occurred > 28 days prior.
 - Patients who discontinue study treatment for reasons other than treatment failure and have not withdrawn consent from overall study participation, should continue to be followed for disease response assessments until the time of disease progression/relapse or the initiation of a new treatment regimen. Patients who have stopped FT-2102 treatment for HSCT should continue to be followed until disease progression/ relapse. This information should be documented on the appropriate eCRF page
- Study drug diary should be distributed by the site to the subject at each clinic visit and collected at the next clinic visit.
- ^q Single agent (FT-2102): FT-2102 will be given in accordance with dosing schedule × 28 days out of 28 days. On C1D1 only a single dose of FT-2102 is taken.
- Combination agent (FT-2102 + azacitidine): azacitidine will be administered via subcutaneous injection or intravenous infusion in combination with oral FT-2102 for 7 days, and then azacitidine will be stopped for 21 days; a 48-hr dose interruption of the azacitidine for weekends or holidays is allowed. On all days and cycles when FT-2102 and azacitidine are co-administered, it is recommended to dose FT-2102 prior to azacitidine.
- After a patient discontinues study treatment and has completed their last study treatment visit, the study site may contact the patient approximately every 3 months to collect survival data and data pertaining to any other alternative anti-neoplastic therapy the patients begins for up to 12 months from the time of their 1st dose of study drug for the Phase 1 part of the study and up to 36 months for the Phase 2 part of the study. Patients who discontinue for reasons other than disease progression or who withdraw consent will continue to be followed for response until progression occurs.

Appendix 3 ECOG Performance Status

Grade	ECOG Performance Status
0	Fully active, able to carry on all pre-disease performance without restriction
1	Restricted in physically strenuous activity but ambulatory and able to carry out work of a light or sedentary nature, eg, light house work, office work
2	Ambulatory and capable of all self-care but unable to carry out any work activities; up and about more than 50% of waking hours
3	Capable of only limited self-care; confined to bed or chair more than 50% of waking hours
4	Completely disabled; cannot carry on any self-care; totally confined to bed or chair
5	Dead

Source: Oken et al. 1982.

Appendix 4 National Cancer Institute Common Terminology Criteria for Adverse Events (NCI CTCAE) Version 4.03

The NCI CTCAE version 4.03 can be found by going to the following web site:

http://ctep.cancer.gov/reporting/ctc.html

Copies of the spiral-bound book of the NCI CTCAE Version 4.03 have been obtained from CTEP/DCT/NCI and are on file for AE classification by site clinical trial, nursing and medical staffs and in the Sponsor's clinical and data management offices.

Inquiries specifically regarding the Common Toxicity Criteria (CTC) should be addressed to: [contact]

